8.4.2 Safety Endpoints

The primary safety objective of this trial is to characterize the safety and tolerability of pembrolizumab in subjects with mCRPC. The primary safety analysis will be based on subjects who experienced toxicities as defined by CTCAE criteria. Safety will be assessed by quantifying the toxicities and grades experienced by subjects who have received pembrolizumab, including serious adverse events (SAEs) and events of clinical interest (ECIs).

Safety will be assessed by reported adverse experiences using CTCAE, Version 4.0. The attribution to study treatment, time-of-onset, duration of the event, its resolution, and any concomitant medications administered will be recorded. AEs will be analyzed including but not limited to all AEs, SAEs, fatal AEs, and laboratory changes.

8.5 Analysis Populations

Subjects will be entered into the trial when they are assigned an allocation number by the IVRS/IWRS.

8.5.1 Efficacy Analysis Populations

The All Subjects as Treated (ASaT) population will serve as the primary population for the analysis of efficacy data in this study. The ASaT population consists of all allocated subjects who received at least one dose of study treatment.

The analysis of DCR, PSA response rate, time to PSA progression, time to initiation of cytotoxic chemotherapy, time to new-anticancer therapy, time to first skeletal-related event, rPFS, and OS will be based on the ASaT population.

The analysis of ORR will be based on all subjects with measurable disease at baseline in the ASaT population.

The analysis of DOR will be based on all responders with measurable disease at baseline in the ASaT population.

The analysis of duration of PSA response will be based on all PSA responders with at least 50% decline from baseline measured twice at least 3 weeks apart. The primary analysis will comprise all subjects with measurable PSA at baseline; the secondary analysis will comprise all subjects with elevated PSA at baseline as a sensitivity analysis.

8.5.2 Safety Analysis Populations

The All Subjects as Treated (ASaT) population will be used for the analysis of safety data in this study. The ASaT population consists of all allocated subjects who received at least one dose of study treatment.

At least one laboratory or vital sign measurement obtained subsequent to at least one dose of study treatment is required for inclusion in the analysis of each specific parameter. To assess change from baseline, a baseline measurement is also required.

8.5.3 Biomarker Discovery Population

The biomarker discovery population consists of the first 100 subjects with RECIST1.1-measurable disease in Cohorts 1 and 2 who are clinically evaluable, which is defined as any subjects who received at least one dose of study drug and had at least 3 post-baseline scans, or discontinued due to radiographic/clinical progression or death before reaching Week 27.

The biomarker discovery population will be used in this study for the evaluation of the association between biomarker score and clinical efficacy and subsequently to determine a biomarker cut-point (if applicable and necessary). The biomarker discovery population will be excluded from any subsequent validation analyses for any biomarker selected population, if applicable. These subjects will still be included in the general efficacy analyses for combined cohorts and by each cohort irrespective of biomarker status.

8.6 Statistical Methods

Statistical testing and inference for safety analyses are described in Section 8.6.2. In addition, separate SAPs will describe the analysis of Pharmacokinetic (PK) data described in Section 7.1.3.2 and a biomarker analysis plan.

8.6.1 Statistical Methods for Efficacy Analyses

This section describes the statistical methods that address the primary and secondary objectives. Methods related to exploratory objectives will be described in the supplemental SAP.

For ORR, DCR and PSA response rate, the point estimate and 95% confidence interval will be provided using the exact binomial method proposed by Clopper and Pearson (1934). Subjects in the analysis population without response data will be counted as non-responder.

For rPFS, DOR, time to PSA progression, duration of PSA response, time to initiation of cytotoxic chemotherapy, time to new-anticancer therapy, time to first skeletal-related event, and OS, Kaplan-Meier (KM) curves and median estimates from the KM curves will be provided as appropriate.

Censoring rules for DOR are summarized in [Table 8](#).

Table 8 Censoring Rules for DOR

Situation	Date of Progression or Censoring	Outcome
No progression nor death, no new anti-cancer therapy initiated	Last adequate disease assessment	Censor (non-event)
No progression nor death, new anti-cancer therapy initiated	Last adequate disease assessment before new anti-cancer therapy initiated	Censor (non-event)
Death or progression after ≥ 2 missed adequate disease assessments	Last adequate disease assessment prior to the after ≥ 2 missed adequate disease assessments	Censor (non-event)
Death or progression after ≤ 1 missed adequate disease assessments	PD or death	End of response (Event)
Subjects are considered to have an ongoing response if censored, alive, have not progressed, have not started a new anti-cancer therapy and have not been determined to be lost to follow-up		

Table 9 summarizes the key efficacy analyses.

Table 9 Analysis Strategy for Key Efficacy Variables

Endpoint/Variable (Description, Time Point)	Statistical Method	Analysis Population	Missing Data Approach
ORR per RECIST 1.1 assessed by central imaging vendor	Exact method based on binomial distribution (Clopper-Pearson method)	Subjects with measurable disease at baseline in ASaT in all below populations 
 • Cohorts 1 and 2 • Cohort 1 • Cohort 2 • Cohort 4 	Subjects with missing data are considered non-responders
DOR per RECSIT 1.1 and per PCWG3-modified RECIST 1.1 assessed by central imaging vendor	Summary statistics using Kaplan-Meier method	Responders with measurable disease at baseline in ASaT in all below populations 
 • Cohorts 1 and 2 • Cohort 1 • Cohort 2 • Cohort 4 	Details are provided in a separate table

Endpoint/Variable (Description, Time Point)	Statistical Method	Analysis Population	Missing Data Approach
DCR per PCWG3-modified RECIST 1.1 assessed by central imaging vendor	Exact method based on binomial distribution (Clopper-Pearson method)	ASaT 
 • Cohorts 1+2+3 • Cohorts 1+2 • Cohorts 4+5 • Each Cohort 	Subjects with missing data are considered disease not under control
PSA Response Rate	Exact method based on binomial distribution (Clopper-Pearson method)	ASaT 
 • Cohorts 1+2+3 • Cohorts 1+2 • Cohorts 4+5 • Each Cohort 	Subjects with missing data are considered non-responders
Time to PSA Progression	Summary statistic using Kaplan-Meier method	ASaT 
 • Cohorts 1+2+3 • Cohorts 1+2 • Cohorts 4+5 • Each Cohort 	Censored at last assessment date
Radiographic PFS per PCWG3-modified RECIST 1.1 assessed by central imaging vendor	Summary statistics using Kaplan-Meier method	ASaT 
 • Cohorts 1+2+3 • Cohorts 1+2 • Cohorts 4+5 • Each Cohort 	Censored at last assessment date
OS	Summary statistics using Kaplan-Meier method	ASaT 
 • Cohorts 1+2+3 • Cohorts 1+2 • Cohorts 4+5 • Each Cohort 	Censored at last date known alive
Duration of PSA response	Summary statistics using Kaplan-Meier method	PSA responders in 
 • Cohorts 4 and 5 • Cohort 4 • Cohort 5 	Censored at last assessment date if no new anti-cancer therapy initiated or last adequate disease assessment before new anti-cancer therapy initiated

Endpoint/Variable (Description, Time Point)	Statistical Method	Analysis Population	Missing Data Approach
Time to initiation of cytotoxic chemotherapy	Summary statistics using Kaplan-Meier method	ASaT in 
 • Cohorts 4 and 5 • Cohort 4 • Cohort 5 	Censored at last date known alive
Time to new-anticancer therapy	Summary statistics using Kaplan-Meier method	ASaT in 
 • Cohorts 4 and 5 • Cohort 4 • Cohort 5 	Censored at last date known alive
Time to first skeletal-related event	Summary statistics using Kaplan-Meier method	ASaT in 
 • Cohorts 4 and 5 • Cohort 4 • Cohort 5 	Censored at last date known alive

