3.2 Secondary Objective(s) & Hypothesis(es)

- 1) **Objective:** To determine the safety and tolerability of pembrolizumab for all cohorts combined (Cohorts 1, 2, 3, 4, and 5) and by each cohort.
- 2) **Objective:** To estimate disease control rate (DCR) and radiographic progression-free survival (rPFS) by PCWG3-modified RECIST 1.1 assessed by central imaging

vendor and PSA response rate, time to PSA progression, and OS for Cohorts 1 and 2 combined, Cohorts 1, 2, and 3 combined, Cohorts 4 and 5 combined, and by each cohort.

- 3) **Objective:** To estimate the duration of response (DOR) by PCWG3-modified RECIST 1.1 in subjects with measurable disease assessed by central imaging vendor in Cohorts 1 and 2 combined, Cohort 1, Cohort 2, and Cohort 4.
- 4) **Objective:** To estimate the duration of response (DOR) by RECIST 1.1 in subjects with measurable disease assessed by central imaging vendor in Cohorts 1 and 2 combined, Cohort 1, Cohort 2, and Cohort 4.
- 5) **Objective:** To estimate duration of PSA response, time to initiation of cytotoxic chemotherapy, time to new-anticancer therapy, and time to first skeletal-related event in Cohorts 4 and 5.

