6.0 TRIAL FLOW CHART

6.1 Study Flow Chart

Trial Period:	Screening Phase	Treatment Cycles ^b								End of Treatment	Post-Treatment		
		1	2	3	4	To be repeated beyond 8 cycles					DC	Safety Follow-up ^c	Follow Up Visits ^d
Treatment Cycle/Title:	Screening (Visit 1) ^a					5	6	7	8	DC	30 days after last dose (±3 days)	Every 9 or 12 weeks (±7 days)	Every 12 weeks (±7 days)
Scheduling Window (Days):	-42 to -1		±3	±3	±3	±3	±3	±3	±3	At time of DC			
Administrative Procedures													
Informed Consent	X ^f												
Informed Consent for FBR (optional)	X												
Inclusion/Exclusion Criteria	X												
Subject Identification Card	X (dispense)									X (collect)			
Demographics and Medical History	X												
Prior and Concomitant Medication Review	X ^g	X	X	X	X	X	X	X	X	X	X ^g		
Trial Treatment Administration		X ^h	X	X	X	X	X	X	X				
Subsequent Anticancer Therapy Status												X	X
Survival Status ⁱ		←-----→									←-----→		X
Clinical Procedures/Assessments													
AE/SAE Monitoring	X	X	X	X	X	X	X	X	X	X	X ^j	X ^j	
Full Physical Examination ^k	X									X			
Directed Physical Examination ^k		X	X	X	X	X	X	X	X				
Vital Signs and Weight ^l	X	X	X	X	X	X	X	X	X	X			
12-Lead ECG	X												
ECOG Performance Status	X	X	X	X	X	X	X	X	X ^m	X			
Laboratory Procedures/Assessments: analysis performed by LOCAL laboratory													
PT/INR and PTT/aPTT	X ⁿ												
CBC with Differential ^o	X ⁿ		X	X	X	X	X	X	X	X	X ^p		
Comprehensive Chemistry Panel ^o	X ⁿ		X	X	X	X	X	X	X	X	X ^p		
Urinalysis ^{o,q}	X ⁿ		X ^q		X		X		X	X	X ^p		
T3, FT4 and TSH ^o	X ⁿ		X ^q		X		X		X	X	X ^p		

Trial Period:	Screening Phase	Treatment Cycles ^b								End of Treatment	Post-Treatment		
		1	2	3	4	To be repeated beyond 8 cycles					DC	Safety Follow-up ^c	Follow Up Visits ^d
Treatment Cycle/Title:	Screening (Visit 1) ^a					5	6	7	8				
Scheduling Window (Days):	-42 to -1		±3	±3	±3	±3	±3	±3	±3	At time of DC	30 days after last dose (±3 days)	Every 9 or 12 weeks (±7 days)	Every 12 weeks (±7 days)
Total Testosterone ^o	X ⁿ				X ^r				X	X			
Laboratory Procedures/Assessments: analysis performed by CENTRAL laboratory													
Tumor Marker Assessment (PSA) ^s	X				X			X		X		X	
PSA for Cohorts 4 and 5 ^s	X		X	X	X			X		X		X	
Anti-drug Antibodies (ADA) ^t		X	X		X			X		X			
Pembrolizumab Pharmacokinetics (serum) ^t		X ^u	X		X			X		X			
Blood for CTC		X ^{v, w}								X			
Blood for AR-V7 ^v		X											
Efficacy Measurements													

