- d. Follow-up visits must occur using the same imaging schedule the subject was on during treatment (eg, every 9 weeks [63 days ±7 days] from the date of allocation or every 12 weeks [84 days ±7 days] from the date of allocation). In subjects who discontinue study therapy without documented disease progression, every effort should be made to continue monitoring their disease status by radiologic imaging (CT/MRI and bone scans) and PSA according to the schedule that the subject was on at the time of discontinuation (eg, every 9 or 12 weeks from the date of allocation) until: 1) the start of new anti-cancer treatment, 2) documented disease progression, 3) death or 4) the end of the study, whichever occurs first.
- e. Survival follow-up begins 12 weeks from the time a subject experiences confirmed disease progression or starts a new anti-cancer treatment.
- f. Written consent must be obtained prior to performing any protocol specified procedures. Results of a test performed prior to the subject signing consent are acceptable in lieu of new screening tests if they are a part of routine clinical management and performed within the specified timeframe.
- g. Prior medications: record all medications taken within 28 days prior to the first dose of trial treatment. Concomitant medications: enter new medications started during the trial and up to 30 days after last dose of trial treatment regardless of when the safety follow-up visit occurs. All medications related to reportable SAEs and events of clinical interest (ECIs) should be recorded as defined in Section 7.2.
- h. Trial treatment should begin on the day of treatment allocation or as close as possible to the date on which the subject is allocated, ie, ≤7 days.
- i. After documented local site assessed disease progression, or the start of new anticancer treatment; contacts are approximately every 12 weeks by telephone. Updated survival status may be requested by the Sponsor at any time during the course of the study. Upon Sponsor notification, all participants who do not/will not have a scheduled study visit or study contact during the Sponsor defined time period will be contacted for their survival status (excluding participants that have a death event previously recorded).

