Progression-free-survival (rPFS) is defined as the time from first day of study treatment to the documented disease progression by central imaging vendor where PD in bone-only tumors will be determined by radionuclide bone scan using PCWG3 criteria and PD for all other tumors will be determined using RECIST 1.1 or death due to any cause, whichever occurs first.

- **Overall Survival (OS)**

Overall survival (OS) is defined as the time from first day of study treatment to the time of death.

- **Duration of PSA response (Cohorts 4 and 5 only)**

Duration of PSA response is defined as the time from PSA response, when the PSA value first declines by at least 50% of the baseline (must be confirmed by a second value), to the date of PSA progression at which there is an increase of 25% or more from the nadir PSA, provided the absolute increase from the nadir PDA is at least 2 ng/mL.

- **Time to initiation of cytotoxic chemotherapy (Cohorts 4 and 5 only)**

Time to initiation of cytotoxic chemotherapy is defined as the time from first day of study treatment to the time of initiation of cytotoxic chemotherapy for prostate cancer.

- **Time to new-anticancer therapy (Cohorts 4 and 5 only)**

Time to new-anticancer therapy is defined as the time from first day of study treatment to the time of new-anticancer therapy for prostate cancer

- **Time to first skeletal-related event (Cohorts 4 and 5 only)**

Time to initiation of first skeletal-related event is defined as the time from first day of study treatment to the first skeletal-related event, which is defined as radiation therapy or surgery to bone, pathologic bone fracture, spinal cord compression, or change or antineoplastic therapy to treat bone pain. See Section 8.6.1 for censoring rules.

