- **Radiographic progression-free survival (rPFS) – per PCWG3-modified RECIST 1.1 assessed by central imaging vendor**

Progression-free-survival (rPFS) is defined as the time from first day of study treatment to the documented disease progression by central imaging vendor where PD in bone-only tumors will be determined by radionuclide bone scan using PCWG3 criteria and PD for all other tumors will be determined using RECIST 1.1 or death due to any cause, whichever occurs first.

- **Overall Survival (OS)**

Overall survival (OS) is defined as the time from first day of study treatment to the time of death.

- **Duration of PSA response (Cohorts 4 and 5 only)**

Duration of PSA response is defined as the time from PSA response, when the PSA value first declines by at least 50% of the baseline (must be confirmed by a second value), to the date of PSA progression at which there is an increase of 25% or more from the nadir PSA, provided the absolute increase from the nadir PSA is at least 2ng/mL.

- **Time to initiation of cytotoxic chemotherapy (Cohorts 4 and 5 only)**

Time to initiation of cytotoxic chemotherapy is defined as the time from first day of study treatment to the time of initiation of cytotoxic chemotherapy for prostate cancer.

- **Time to new-anticancer therapy (Cohorts 4 and 5 only)**

Time to new-anticancer therapy is defined as the time from first day of study treatment to the time of new-anticancer therapy for prostate cancer

- **Time to first skeletal-related event (Cohorts 4 and 5 only)**

Time to initiation of first skeletal-related event is defined as the time from first day of study treatment to the first skeletal-related event, which is defined as radiation therapy or surgery to bone, pathologic bone fracture, spinal cord compression, or change or antineoplastic therapy to treat bone pain.

See [Section 3.6.1](#) for censoring rules.

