### 3.6 Statistical Methods

#### 3.6.1 Statistical Methods for Efficacy Analyses

For ORR, DCR and PSA response rate, the point estimate and 95% confidence interval will be provided using the exact binomial method proposed by Clopper and Pearson (1934) [3]. Subjects in the analysis population without response data will be counted as non-responders.

For rPFS, DOR, time to PSA progression, duration of PSA response, time to initiation of cytotoxic chemotherapy, time to new-anticancer therapy, time to first skeletal-related event, and OS, Kaplan-Meier (KM) curves and median estimates from the KM curves will be provided as appropriate.

Censoring rules for DOR are summarized in [Table 1](#).

Table 1 Censoring Rules for DOR

Situation	Date of Progression or Censoring	Outcome
No progression nor death, no new anti-cancer therapy initiated	Last adequate disease assessment	Censor (non-event)
No progression nor death, new anti-cancer therapy initiated	Last adequate disease assessment before new anti-cancer therapy initiated	Censor (non-event)
Death or progression immediately after $\geq 2$ consecutive missed disease assessments or after new anti-cancer therapy, if any	Earlier date of last adequate disease assessment prior to $\geq 2$ missed adequate disease assessments and new anti-cancer therapy, if any	Censor (non-event)
Death or progression after $\leq 1$ missed disease assessments and before new anti-cancer therapy, if any	PD or death	End of response (Event)
A missed disease assessment includes any assessment that is not obtained or is considered inadequate for evaluation of response.		

Censoring rules for rPFS are summarized in [Table 2](#).

Table 2 Censoring Rules for Analyses of rPFS

Situation	Rule
PD or death documented after $\leq 1$ missed disease assessment, and before new anti-cancer therapy, if any	Progressed at date of documented PD or death
PD or death documented immediately after $\geq 2$ consecutive missed disease assessments or after new anti-cancer therapy, if any	Censored at last disease assessment prior to the earlier date of $\geq 2$ consecutive missed disease assessment and new anti-cancer therapy, if any
No PD and no death; and new anticancer treatment is not initiated	Censored at last disease assessment
No PD and no death; new anticancer treatment is initiated	Censored at last disease assessment before new anticancer treatment

[Table 3](#) summarizes the key efficacy analyses.

Table 3 Analysis Strategy for Key Efficacy Variables

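### Time to chemotherapy and time to new anticancer therapy (Cohorts 4 and 5) are to be estimated by Kaplan-Meier with event-free deaths censored, which overstates how many subjects start therapy and how soon

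*Protocol*

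**What the plan says.** Secondary objective 5 (Protocol 3.2) is to estimate, along with duration of PSA response, "time to initiation of cytotoxic chemotherapy, time to new-anticancer therapy, and time to first skeletal-related event in Cohorts 4 and 5". Protocol 8.4.1 defines the first of these as "the time from first day of study treatment to the time of initiation of cytotoxic chemotherapy for prostate cancer". sSAP 3.4.1 defines the second as "the time from first day of study treatment to the time of new-anticancer therapy for prostate cancer". Death is part of neither definition, nor of the skeletal-event definition. By contrast, the rPFS and DOR definitions in the same sections name death from any cause as an event.

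For the method, the Protocol sentence covers "time to initiation of cytotoxic chemotherapy, time to new-anticancer therapy, time to first skeletal-related event, and OS, Kaplan-Meier (KM) curves and median estimates", and sSAP 3.6.1 repeats that "Kaplan-Meier (KM) curves and median estimates from the KM curves will be provided as appropriate". In Protocol Table 9 and sSAP Table 3, the rule for all three endpoints is "Censored at last date known alive". The sSAP revised its censoring rules for rPFS and DOR only. Neither document names a competing-risk estimator, a composite with death, or a target in which deaths are hypothetically removed.

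**The concern.** All subjects are followed for survival until death, withdrawal of consent or the end of the study (Protocol 2.1), so deaths before the event will be observed. Under the stated rule, such a subject leaves the risk set as a censored observation. Kaplan-Meier then assumes that his later risk of starting therapy equals that of the men still alive, although he can no longer start. The resulting curve does not describe what happens to the cohort.

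The objective is estimation and there is no control arm, so these curves and medians are the deliverable and nothing offsets a systematic error. A reader would naturally take the median as the time by which half of the subjects had moved on to further treatment.

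**Working it through.** **Inputs from the documents.** Event definitions: Protocol 8.4.1, sSAP 3.4.1. Estimator and censoring: Protocol 8.6.1 and Table 9, sSAP 3.6.1 and Table 3. Sizes: about 80 in Cohort 4 and 40 in Cohort 5 (Protocol 8.9), 120 together. The plan states no event rate, death rate or median for these endpoints, so there is no figure of its own to reproduce. All rates below are assumptions.

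**Step 1: direction.** At each therapy start with r subjects at risk, 1-KM rises by K/r, where K is the Kaplan-Meier estimate just before it with deaths censored. The Aalen-Johansen estimate rises by S/r, where S is the estimate of being alive and event-free. Deaths lower S but not K, so K ≥ S. In any data set 1-KM is therefore at or above the cumulative incidence, and the KM median cannot fall later than the time to 50% incidence. The two agree only if no event-free death precedes a later event. This step assumes that therapy status is known up to the censoring date.

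**Step 2: size under constant independent hazards.** Let a = ln2/(event median), b = ln2/(death median).
- 1-KM(T) = 1 − exp(−aT)
- CIF(T) = a/(a+b) × [1 − exp(−(a+b)T)]
- Time to CIF 50% = −ln(1 − 0.5(a+b)/a)/(a+b), not reached if b ≥ a

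Worked case, event median 12 and death median 24: a = 0.05776, b = 0.02888, a/(a+b) = 2/3. At 12 months, 1-KM = 50.0% and CIF = 2/3 × (1 − exp(−1.0397)) = 2/3 × 0.6464 = 43.1%. Time to 50% = −ln(0.25)/0.08664 = 16.0 months.

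Event median 12 months:

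| Death median (months) | CIF at 12 (1-KM 50.0%) | CIF at 18 (1-KM 64.6%) | Time to 50% (KM median 12.0) |
|---|---|---|---|
| 24 | 43.1% | 52.7% | 16.0 |
| 36 | 45.2% | 56.2% | 14.3 |
| 60 | 47.1% | 59.4% | 13.2 |

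Over event medians 6, 9, 12 and 18 and death medians 24, 36 and 60, the gap runs from 2.3 points (18 and 60) to 9.1 (6 and 24) at 12 months, and from 4.3 to 13.4 at 18 months for the same two combinations.

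**Step 3: dependence.** If the two hazards share a gamma frailty of variance 0.5 to 1.0, the gap over the same grid is 1.5 to 6.1 points at 12 months and 2.5 to 8.7 at 18. It shrinks but keeps its sign.

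**Step 4: against sampling error.** In simulated trials (event median 12, follow-up uniform on 12 to 24 months) the standard error of the 12-month cumulative incidence at n=120 is about 4.6 points. The low end of the gap is below that. At n=40, among trials that reach 50% incidence, the KM median is earlier in 93/83/57% for death medians 24/36/60, with a typical shift of about 2.1/1.1/0.2 months.

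**The case against.** The strongest reply is that the target is being assumed. The objective speaks of time to an event. The plan promises KM curves and medians as appropriate, and sets no 12- or 18-month landmark for these endpoints. Kaplan-Meier with deaths censored estimates a recognised net quantity, and labelling it and tabulating event-free deaths would cure much of the problem. That stands in part: it would be too strong to infer that Kaplan-Meier is invalid here. But the plan does not say that a deaths-removed quantity is intended, and that quantity needs an independence assumption that the documents do not discuss.

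Second, the censoring of deaths is inferred. The rule sits in a column on missing data, and the OS row uses the same words. This is fair, but death is omitted from these definitions and named for rPFS and DOR, and no other rule covers an untreated death.

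Third, the size is wholly assumed, and the ordering of the two medians is close to automatic, so how often it appears in simulations says nothing about importance. Both points stand. OS will be reported for the same cohorts, but it does not show how many died before starting therapy.

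A reader might also infer an opposite bias from the flow-chart footnote "Updated survival status may be requested by the Sponsor at any time during the course of the study", reasoning that survival-only contacts add time counted as therapy-free. The documents do not support this: they do not say that therapy status goes unasked at those contacts, and the flow chart schedules "Subsequent Anticancer Therapy Status" in both follow-up and survival follow-up.

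**Conclusion.** The concern holds for the two therapy-start endpoints. As written, and provided therapy status is known to the censoring date, the plan overstates the proportion starting therapy and gives a median no later, and usually earlier, than the time by which half have started. The direction does not depend on the assumed rates; the size does. It is 2.3 to 9.1 points at 12 months and 4.3 to 13.4 at 18 under constant independent hazards, and less under shared frailty. In Cohort 5 alone the shift in the median may be small.

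Time to first skeletal-related event has the same competing-death problem. A reader might go further and infer, from the absence of a flow-chart row for these events, that they are under-recorded and the estimate biased in a known direction. The documents do not settle how long such events are captured, so neither claim is made.

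The consequences are limited to descriptive secondary endpoints. ORR, OS, rPFS and the sample size are unaffected.

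**What to change.** Amend Protocol 8.6.1/Table 9 and sSAP 3.6.1/Table 3 for the three endpoints, in Cohort 4, Cohort 5 and both combined:

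1. Report the Aalen-Johansen cumulative incidence, with death without the event as a competing event, and 95% CIs at fixed times (for example 6, 12 and 18 months).
2. Report the time to 50% cumulative incidence, or state that it is not reached, and the number of event-free deaths.
3. Censor event-free living subjects at the last date on which event status was ascertained.
4. Keep the planned KM curve as supportive, labelled as treating deaths as censored.

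The cost is analysis-plan wording, a derived last-ascertainment date and standard software output. The two therapy endpoints need no new data collection, because therapy status is already scheduled in follow-up. There are two small downsides. Comparison with publications that censored deaths is less direct, which the supportive curve covers. The 50% point will also sometimes not be reached: in the simulations above it was reached in 91/99/100% of trials at n=120 and 77/89/95% at n=40 (death medians 24/36/60).
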